3.2 OUTCOME MEASURES

3.2.1 Primary Outcome Measures

- Assessment of safety and tolerability of NAC including incidence and severity of systemic and ocular adverse events (AEs) and changes from baseline vital signs and physical examination.

3.2.2 Secondary Outcome Measures

- Change from baseline aqueous and serum carbonyl content and GSH/GSSG ratio at 1, 2, 3, 4, 5, 6, 7, 8 and 9 months after initiation of NAC.
- Change from baseline BCVA 6 months after initiation of NAC.
- Change from baseline central retinal sensitivity by microperimetry 3, 6, and 9 months after initiation of NAC.
- Change from baseline ellipsoid zone (EZ) width by SD-OCT 6 month after initiation of NAC .

3.3 SAFETY PLAN

The safety assessments to be conducted for this study are listed in Section 5

Potential safety issues are associated with anterior chamber taps and peripheral blood draw. Subjects will be instructed to contact their physician at any time should they have health-related concerns. All adverse events (serious and non-serious) will be recorded for up to 14 days after the last study visit.

Anterior chamber tap in the clinic in patients with RP

The patient will be seated at a slit lamp and a drop of topical anesthetic will be placed in the study eye. A 30 gauge needle will be passed through the limbus into the anterior chamber and 0.15 ml of aqueous humor will be removed. There are no nerves at the limbus below the epithelium and therefore the topical anesthetic provides complete anesthesia and there is no pain associated with the procedure. Anterior chamber tap is a routine procedure that is extremely safe. It is done to deal with severe

increased intraocular pressure after intravitreal injections, or injection of gas during pneumatic retinopexy. Anterior chamber taps have been done as part of several prior studies and there have been no related complications or adverse events.

Peripheral blood draw

The peripheral blood will be drawn to collect RNA and DNA samples and serum bilirubin levels at the screening visit (BL-28 to 56 days). Blood draw for measurement of serum carbonyl content and GSH/GSSG ratio will be performed at each study visit. At the baseline (Day 1 +7days), week 12 and week 24 visit, peripheral blood will be drawn before as well as 1 and 2 hours after administration of oral NAC in the clinic for measurement of plasma NAC levels. The 2 hour blood draw will be optional, based on the convenience of the subject and at the discretion of the investigator. The peripheral blood draw is commonplace procedure and there are no risks to exposure to transmissible diseases if ones blood is being drawn using aseptic conditions. A patient may feel light headed or faint, or experience pain or discomfort at the site of puncture during the procedure. There may be possible bruising or swelling at the puncture site, rarely there may be an infection.

The Principal Investigator will review all adverse events on an ongoing basis. JHU IRB 3 will be notified immediately of any serious adverse events and will be notified in yearly renewals of all other adverse events. The IRB will be notified of any interruption in enrollment or change in the conduct of the study.

3.4 COMPLIANCE WITH LAWS AND REGULATIONS

This study will be conducted in accordance with current U.S. Food and Drug Administration (FDA) Good Clinical Practices (GCPs), and local ethical and legal requirements.

4. **MATERIALS AND METHODS**

4.1 **SUBJECTS**

4.1.1 **Subject Selection**

Thirty eligible subjects with RP will be enrolled. Subjects will be identified and recruited through the clinic population at the Wilmer Eye Institute and it is expected that enrollment will be completed over an 12 month period.

4.1.2 **Inclusion Criteria**

All subjects must meet the following criteria to be eligible for study entry:

- Signed informed consent and authorization of use and disclosure of protected health information
- Age ≥ 18 years
- Patients diagnosed with RP by the investigators, based on clinical phenotype and diagnostic tests

4.1.3 **Exclusion Criteria**

Subjects who meet any of the following criteria will be ineligible for study entry:

- Patients with concurrent retinal pathologies that result in vision loss, including but not limited to retinal vein occlusion, diabetic retinopathy and neovascular age-related macular degeneration. If one eye does not have any retinal pathology other than RP, it may be enrolled in the study.
- Patients with uncontrolled arterial hypertension defined as diastolic blood pressure > 95 mm Hg or systolic blood pressure > 160 mm Hg despite medical therapy.

4.2 **STUDY ASSESSMENTS**

For a complete overview of the study assessments, see Flow Charts in Appendix section.

Screening Visit

- Obtain Informed Consent
- Record demographics, medical and ocular history; concomitant medications, smoking history, alcohol intake and supplement usage

- Vital sign measurements (blood pressure, pulse rate, temperature and respiratory rate)
- Slit lamp examination
- Indirect Ophthalmoscopy
- BCVA by Early Treatment Diabetic Retinopathy Study (ETDRS) Protocol
- SD-OCT
- Fundus autofluorescence
- Ultrawide field fundus photography
- MP1 and MAIA microperimetry
- Anterior chamber tap (for measurement of carbonyl content and GSH/GSSG)
- Blood draw for RNA and DNA samples, serum carbonyl content, GSH/GSSG ratio and bilirubin levels.

Baseline Visit (Day 1)

- Record any change in medical and ocular history; concomitant medications, smoking history, alcohol intake, supplement usage and adverse events
- Vital sign measurements (blood pressure, pulse rate, temperature and respiratory rate)
- Slit lamp examination
- Indirect Ophthalmoscopy
- BCVA by Early Treatment Diabetic Retinopathy Study (ETDRS) Protocol
- SD-OCT
- MP1 and MAIA microperimetry
- Anterior chamber tap (for measurement of carbonyl content and GSH/GSSG)
- Obtain blood for serum carbonyl content, GSH/GSSG ratio and blood for plasma NAC Levels (before and after drug administration).
- Initiation of NAC treatment, first dose of NAC to be administered in the clinic

Four Week Visit (Week 4/ 28±7days)

- Record any change in medical and ocular history; concomitant medications, smoking history, alcohol intake, supplement usage and adverse events
- Vital sign measurements (blood pressure, pulse rate, temperature and respiratory rate)

- Slit lamp examination
- Indirect Ophthalmoscopy
- BCVA
- MAIA microperimetry
- Anterior chamber tap (for measurement of carbonyl content and GSH/GSSG)
- Blood Draw for serum carbonyl content and GSH/GSSG ratio

Eight Week Visit (Week 8/ 56±7days)

- Record any change in medical and ocular history; concomitant medications, smoking history, alcohol intake, supplement usage and adverse events
- Vital sign measurements (blood pressure, pulse rate, temperature and respiratory rate)
- Slit lamp examination
- Indirect Ophthalmoscopy
- BCVA
- MAIA microperimetry
- Anterior chamber tap (for measurement of carbonyl content and GSH/GSSG)
- Blood Draw for serum carbonyl content and GSH/GSSG ratio

Twelve Week Visit (Week 12/ 84±7days)

- Record any change in medical and ocular history; concomitant medications, smoking history, alcohol intake, supplement usage and adverse events
- Vital sign measurements (blood pressure, pulse rate, temperature and respiratory rate)
- Slit lamp examination
- Indirect Ophthalmoscopy
- BCVA
- SD-OCT
- MAIA microperimetry
- Anterior chamber tap (for measurement of carbonyl content and GSH/GSSG)
- Obtain blood for serum carbonyl content, GSH/GSSG ratio and blood for plasma NAC levels (before and after drug administration).

- NAC to be administered in the clinic

Sixteen Week Visit (Week 16/ 112±7days)

- Record any change in medical and ocular history; concomitant medications, smoking history, alcohol intake, supplement usage and adverse events
- Vital sign measurements (blood pressure, pulse rate, temperature and respiratory rate)
- Slit lamp examination
- Indirect Ophthalmoscopy
- BCVA
- MAIA microperimetry
- Anterior chamber tap (for measurement of carbonyl content and GSH/GSSG)
- Blood Draw for serum carbonyl content and GSH/GSSG ratio

Twenty Week Visit (Week 20/ 140±7days)

- Record any change in medical and ocular history; concomitant medications, smoking history, alcohol intake, supplement usage and adverse events
- Vital sign measurements (blood pressure, pulse rate, temperature and respiratory rate)
- Slit lamp examination
- Indirect Ophthalmoscopy
- BCVA
- MAIA microperimetry
- Anterior chamber tap (for measurement of carbonyl content and GSH/GSSG)
- Blood Draw for serum carbonyl content and GSH/GSSG ratio

Twenty-Four Week Visit (Week 24/ 168±7days)

- Record any change in medical and ocular history; concomitant medications, smoking history, alcohol intake, supplement usage and adverse events
- Vital sign measurements (blood pressure, pulse rate, temperature and respiratory rate)
- Slit lamp examination
- Indirect Ophthalmoscopy

- BCVA
- SD-OCT
- Fundus auto-fluorescence
- Ultra-wide field fundus photography
- MAIA microperimetry
- Anterior chamber tap (for measurement of carbonyl content and GSH/GSSG)
- Blood Draw for serum carbonyl content, GSH/GSSG ratio and blood for plasma NAC levels (before and after drug administration)
- NAC to be administered in the clinic

Twenty-Eight Week Visit (Week 28/ 196±7days)

- Record any change in medical and ocular history; concomitant medications, smoking history, alcohol intake, supplement usage and adverse events
- Vital sign measurements (blood pressure, pulse rate, temperature and respiratory rate)
- Slit lamp examination
- Indirect Ophthalmoscopy
- BCVA
- MAIA microperimetry
- Anterior chamber tap (for measurement of carbonyl content and GSH/GSSG)
- Blood Draw for serum carbonyl content and GSH/GSSG ratio

Thirty-Two Week Visit (Week 32/ 224±7days)

- Record any change in medical and ocular history; concomitant medications, smoking history, alcohol intake, supplement usage and adverse events
- Vital sign measurements (blood pressure, pulse rate, temperature and respiratory rate)
- Slit lamp examination
- Indirect Ophthalmoscopy
- BCVA
- MAIA microperimetry
- Anterior chamber tap (for measurement of carbonyl content and GSH/GSSG)

- Blood Draw for serum carbonyl content and GSH/GSSG ratio

Thirty-Six Week Visit (Week 36/ 252+7days)

- Record any change in medical and ocular history; concomitant medications, smoking history, alcohol intake, supplement usage and adverse events
- Vital sign measurements (blood pressure, pulse rate, temperature and respiratory rate)
- Slit lamp examination
- Indirect Ophthalmoscopy
- BCVA
- SD-OCT
- MAIA microperimetry
- Anterior chamber tap (for measurement of carbonyl content and GSH/GSSG)
- Blood Draw for serum carbonyl content and GSH/GSSG ratio

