Oxidative damage has been implicated in several diseases including cystic fibrosis, chronic obstructive pulmonary disease (COPD), and Idiopathic Pulmonary Fibrosis. NAC also has a mucolytic effect which makes it particularly useful for treatment of these pulmonary diseases. The effect of oral NAC has been tested in these indications in several clinical trials providing extensive safety data. In COPD, NAC 600mg bid improves airway function and reduces the frequency of acute exacerbations.[14, 15] Doses of up to 1800mg/day have been well-tolerated in the treatment of Idiopathic Pulmonary Fibrosis.[16] Paracetamol (acetaminophen) toxicity is treated with a loading dose of 140 mg/kg NAC followed by 70 mg/kg every 4 hours for 17 doses.[17] Normal volunteers tolerated a dose of 11.2 grams NAC/day for three months without any serious undesirable effects [18] and in another study a dose of 500mg/kg/day was tolerated.[19] The most frequent adverse events associated with the oral administration of NAC are

gastrointestinal in nature and include vomiting, diarrhea, stomatitis, abdominal pain and nausea (incidence rate $\geq 1/1000$ to $< 1/100$). Hypersensitivity reactions including anaphylactic shock and anaphylactic/anaphylactoid reaction (incidence rate $< 1/10,000$), dyspnea, bronchospasm (incidence rate $\geq 1/10,000$ to $< 1/1000$), angioedema, tachycardia, urticaria, rash and pruritus (incidence rate $\geq 1/1000$ to $< 1/100$) have been reported less frequently. Finally, reports of headache, tinnitus, pyrexia, blood pressure decreased (incidence rate $\geq 1/1000$ to $< 1/100$), face edema and hemorrhage have also been collected with oral NAC. In this study, we will use NAC 600 mg effervescent tablets which are generally more pleasant and more tolerable than large capsules; however, because the formulation contains sodium, we will exclude patients with uncontrolled arterial hypertension defined as diastolic blood pressure > 95 mm Hg or systolic blood pressure > 160 mm Hg.

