3. STUDY DESIGN

3. DESCRIPTION OF THE STUDY

This study is a phase 1 dose escalation study with 3 cohorts, designed to assess the safety and tolerability of NAC in subjects with RP. Thirty subjects with RP will be enrolled from the clinic population of the Wilmer Eye Institute, Johns Hopkins. Informed consent will be obtained from all study subjects prior to enrollment. Each cohort will have an experimental and an exploratory arm. Subjects with RP will be enrolled in the experimental arm if they have a high carbonyl content (≥ 0.6) and a reduced GSH/GSSG ratio (≤ 3.0) in the aqueous. Subjects with RP who don't have a high carbonyl content (≥ 0.6) and a reduced GSH/GSSG ratio (≤ 3.0) but otherwise are good candidates for the study will be enrolled in the exploratory arm. The reason for this stratification is that the primary outcome is the change from baseline carbonyl content and GSH/GSSG caused by each dose of NAC and patients who have reduced chance to show improvement could skew the data and reduce the ability to identify the minimally effect dose. In a previous study, 17 of 20 patients with RP fit these criteria, so we anticipate that 8-9 subjects in each cohort will be in the experimental group. We do not want to

completely exclude RP patients who do not fit these criteria, because they may experience substantial decrease in carbonyl content and substantial increase in GSH/GSSG and their inclusion in the exploratory arm will help to determine if patients who do not fit the criteria should be excluded from the next trial, a longer trial with a functional endpoint.

Baseline testing will include: (1) detailed medical and ophthalmological history, (2) measurement of vital signs (3) slit lamp examination, (4) funduscopy examination, (5) best-corrected visual acuity (BCVA), (6) MP1 and MAIA microperimetry, (7) SD-OCT, and (8) ultrawide angle fundus photographs. One eye will be selected as the study eye and an anterior chamber tap will be done for measurement of GSH/GSSG and protein carbonyl content. Serum GSH/GSSG, protein carbonyl content and bilirubin levels will also be measured. Blood will be obtained for RNA and DNA samples. The following is the dosing of NAC 600 mg effervescent tablets in each cohort.

	Baseline	Week 4	Week 8	Week 12	Week 20	Week 24
Cohort 1	600mg bid	600mg bid	600mg bid	600mg tid	600mg tid	600mg tid
Cohort 2	1200mg bid	1200mg bid	1200mg bid	1200mg tid	1200mg tid	1200mg tid

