Cohort 3	1800mg bid	1800mg bid	1800mg bid	1800mg tid	1800mg tid	1800mg tid

There will be 8 study visits (screening, baseline and month 1-6), all study visits after the baseline visit will be 28±7 days apart, followed by a 12 week observation period. At each visit, patients will have medical history, measurement of vital signs (blood pressure, heart rate, respiratory rate and temperature), review of concomitant medications, review of study drug diary, recording of adverse events, BCVA, eye examination, and anterior chamber tap. MP1 microperimetry will be done at screening and baseline visit. Optical Coherence tomography will be done at the screening and baseline visit and repeated every 3 months. MAIA microperimetry will be done at screening and baseline visit and repeated every month. Fundus autofluorescence and Ultrawide field fundus photographs will be obtained at screening and month 6 visit. At all visits where needed, microperimetry will be performed first followed by OCT, FAF and UWFP. Serum levels of NAC pre- and post-dose will be measured at baseline, week 12 and 24. When all 10 subjects in cohort 1 have had a week 4 visit, the PI will review safety and tolerability with study team members and if there has been good safety and tolerability, enrollment will begin for cohort 2. When all 10 subjects in cohort 2 have had a week 4 visit, the PI will

review safety and tolerability with study team members and if there has been good safety and tolerability, enrollment will begin for cohort 3.

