4.3 DOSING AND DOSE ESCALATION

This is a dose-escalation study in which 6 doses of NAC effervescent tablets are being tested: 600mg bid, 600mg tid, 1200mg bid, 1200mg tid, 1800mg bid and 1800mg tid. Patients will be given the dose pre-determined for the cohort they enter upon enrollment. The most common side effect of NAC is nausea and vomiting. If a patient cannot tolerate the assigned dose of NAC due to nausea and/or vomiting, the dose will be reduced to the dose immediately below the current dose. If that dose cannot be tolerated, the dose will be reduced to the next lowest level. This will be done until a tolerated dose is identified and the patient will be maintained on that dose throughout the trial. If a patient cannot tolerate the starting dose of 600mg bid, they will be reduced to 600mg qd. If a patient cannot tolerate a dose of 600mg qd, they will be exited from the trial. If 3 of the first 5 subjects in a cohort or a total of 5 subjects are unable to tolerate a particular dose of NAC, no additional subjects will be treated with that dose and the dose immediately below it will be designated the maximum tolerated dose. All subsequent subjects enrolled in the study will be treated with the maximum tolerated dose.

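### The hypertension exclusion in section 4.1.3 carries a treatment qualifier that the rationale lacks; read literally, it admits an untreated subject at, for example, 170/90 mm Hg

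*Combined protocol and SAP*

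**What the plan says.** The exclusion appears twice.

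- **Section 1.1, Study Rationale.** The reason and the rule are given together: "because the formulation contains sodium, we will exclude patients with uncontrolled arterial hypertension defined as diastolic blood pressure > 95 mm Hg". The sentence goes on to give a systolic limit of 160 mm Hg. Whether the patient is on treatment plays no part.
- **Section 4.1.3, Exclusion Criteria.** The same term is defined with the same two limits, but the definition closes with a qualifier: "systolic blood pressure > 160 mm Hg despite medical therapy".

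No other section defines the criterion, says how a patient with untreated high pressure is handled, or calls for treatment and re-measurement before entry. Section 4.1.3 has only two exclusions. The other concerns retinal disease, so this is the only one directed at systemic safety.

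After entry, blood pressure is followed. Section 3 states: "At each visit, patients will have medical history, measurement of vital signs (blood pressure, heart rate, respiratory rate and temperature". The primary outcome in section 3.2.1 includes "changes from baseline vital signs and physical examination".

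**The concern.** Section 4.1.3 is the text that decides eligibility at screening. Its qualifier makes current treatment part of the definition of the excluded condition. A subject at 170/90 on antihypertensives is kept out, while a subject with the same reading who takes nothing is, on the literal wording, let in. The stated reason for the exclusion, sodium in the tablets, makes no such distinction.

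Two investigators could therefore decide differently on the same patient. At stake is whether a person whom the rationale meant to keep off a sodium-containing formulation could be started on it. It is a question of patient protection and consistent eligibility, not of inference.

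**Working it through.** No figure in the plan needs reproducing. The check sets the two wordings side by side and applies them to test subjects.

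**Inputs.** Diastolic limit 95 mm Hg and systolic limit 160 mm Hg, identical in sections 1.1 and 4.1.3. The treatment qualifier is in 4.1.3 only.

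**Rules**, with D = diastolic, S = systolic, T = on medical therapy:

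- Rationale: exclude if D > 95 or S > 160.
- 4.1.3, reading A (qualifier attaches to the systolic limit only): exclude if D > 95, or if S > 160 and T.
- 4.1.3, reading B (qualifier attaches to both limits): exclude if (D > 95 or S > 160) and T.

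**Results.** The pressures are illustrations chosen to fall on either side of the limits.

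| Subject | Rationale | 4.1.3, reading A | 4.1.3, reading B |
|---|---|---|---|
| 170/90, untreated | exclude | admit | admit |
| 150/100, untreated | exclude | exclude | admit |
| 170/100, untreated | exclude | exclude | admit |
| 170/90, treated | exclude | exclude | exclude |
| 150/100, treated | exclude | exclude | exclude |
| 150/90, either | admit | admit | admit |

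**What follows.**

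1. Within both limits, or above a limit and on therapy, the two sections agree.
2. They can differ only for subjects who are above a limit and untreated.
3. Within that group, the conflict holds under both readings only when S > 160 and D is 95 or below. Where D > 95, reading A excludes the subject through the diastolic limit and reading B does not, so the outcome turns on how the sentence is parsed.

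**The case against.** The strongest reply is that the criterion opens with the word uncontrolled, and that a sensible investigator would regard untreated pressure of 170/90 as uncontrolled and exclude the patient. Screening records blood pressure, medical history and concomitant medications, so such a patient would be visible. This stands in part: it makes the defect an ambiguity and not a proven path to enrolment. It does not remove it, because 4.1.3 supplies its own definition of the term and puts the treatment condition inside that definition.

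A second reply is that background text often shortens a criterion, and that the qualifier may be deliberate: treat first, then reassess. That is possible, but no section describes such a path, so an untreated patient is left without an instruction.

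A third reply is that safeguards follow entry. Besides the blood pressure checks, a week-4 review precedes the next cohort ("if there has been good safety and tolerability, enrollment will begin for cohort 2"), and section 3.3 says: "The Principal Investigator will review all adverse events on an ongoing basis". Under sections 5.1 and 5.2 a chronic condition that worsens is recorded as an adverse event, so worsening hypertension would reach that review. Section 5.3.5 allows drug to be held, and section 4.4 allows the study to be stopped. All of this stands and limits the consequence. None of these provisions gives a blood pressure value, however, and the dose-reduction rule in section 4.3 responds to nausea and vomiting. The 95 and 160 mm Hg entry limits are the only numeric ones in the document.

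A reader might also infer more than the text supports:

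- *That every untreated subject above 160 systolic is eligible.* This is secure only when diastolic pressure is 95 or below; at 170/100, reading A excludes.
- *That sodium carries the same risk in treated and untreated patients.* The rationale gives sodium as the reason and is silent on treatment; it makes no claim about relative risk.
- *That the dose range shows the size of the problem.* With 600 mg tablets, assigned intake runs from 2 a day (600 mg bid: 1200/600) to 9 a day (1800 mg tid: 5400/600). That describes the dosing of every subject, whatever 4.1.3 says, and sodium per tablet is not given.
- *That the plan errs by not applying the limits again on Day 1.* The plan is silent there, which is not an error.

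**Conclusion.** The point holds as an ambiguity in wording. Sections 1.1 and 4.1.3 define the same exclusion differently, and the literal reading of the operative one runs against the safety reason that the plan gives. The conflict is certain for untreated subjects above 160 systolic with diastolic pressure of 95 or below, and depends on parsing for untreated subjects with diastolic pressure above 95.

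Its size in practice cannot be stated. The documents do not say how many of the 30 subjects might be untreated and above a limit; the number may be zero, and the added risk cannot be quantified. Sample size, power and analysis are unaffected. The conclusion assumes that 4.1.3 governs enrolment and that the rationale shows what the exclusion was for. It does not support a claim that such patients will be enrolled. The change is a cheap improvement in patient safety, at the level of something to consider.

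**What to change.** In section 4.1.3, delete the last three words of the hypertension criterion, so that it excludes the same patients as the rationale. Alternatively, replace them with: whether or not on medical therapy. Either change also removes the parsing question.

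The cost is a minor text change and an occasional extra screen failure. The sponsor may also wish to allow re-screening once pressure is controlled to within both limits, at the price of a repeat visit. That would be a new provision, found in neither section, and the correction does not depend on it.
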